3.6 Sample Size and Statistical Considerations

The planned sample size for the trial is 320 randomized patients. Sixteen of these 320 patients will come from the FLU-IVIG Pilot. A sample size re-estimation will be made after approximately 150 patients have been enrolled.

The following assumptions were made in estimating the required sample size for the trial:

a. The primary analysis will be intention to treat with a proportional odds model that includes indicators for treatment group and indicators for whether the patient was enrolled in the ICU and required oxygen at the time of

randomization. The model will be stratified by geographic region (United States, Europe, South America and Australasia).

- b. Type 1 error is 0.05 (2-sided) and power =0.80.
- c. Patients will be equally allocated to IVIG or placebo.
- d. The clinical status of patients in the control arm at Day 7 will be similar to patients enrolled in the hospital in FLU 003 (see section 2.1 and table below). The estimates from FLU 003 are based on 333 hospitalized patients who were enrolled 7 or fewer days after onset of influenza symptoms and who had a NEW score of 2 or greater at the time of enrollment.
- e. In FLU 003, approximately 64-65% of patients were out of the hospital on Day 7 (sum of 39.0% and 25.8% in table). We assumed that for patients given IVIG this percent could be increased to 74% (about 10 percentage points). We assumed this same proportional improvement (an odds ratio of approximately 1.6) would apply to other category cutpoints on the ordinal scale (an underlying assumption of the proportional odds model). If that were the case, the percentages in each clinical state in the IVIG group that would be realized are shown Table 2.⁴⁴
- f. Based on the FLU-IVIG Pilot, we expect minimal non-adherence to IVIG and missing data at Day 7.

Table 2: Difference that Can Be Detected in the Day 7 Ordinal Outcome

Power = 80%, Alpha = .05 (2-sided) and Sample Size = 320

1 01101 0070,711,0114 100 (2 01	 ., u.i.a. capic c.		
	Day 7 Outcome (%)		
Hierarchical Outcome	Placebo	IVIG	
Death	1.8	1.0	
In ICU	3.6	2.1	
Non-ICU hospitalization, on O2	15.6	9.9	
Non-ICU hospitalization, not on O2	14.1	10.3	
Not back to normal activities	39.0	38.4	
Resumed normal activities	25.8	38.2	
Odds ratio		1.77	

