6.1 Data Analysis

The primary analysis will be intention to treat, comparing the outcomes of patients assigned IVIG with those assigned placebo. For the primary endpoint, the percent of patients in the following 6 categories will be compared: 1) death; 2) ICU; 3) non-ICU ward, on supplemental oxygen; 4) non-ICU ward, not on supplemental oxygen; 5) out of the hospital but normal activities have not been resumed; and 6) out of the hospital

and normal activities resumed. Patients discharged from the hospital to a rehabilitation facility will be included in category 5) above. Patients discharged from the hospital to a nursing home will also be included in category 5), unless the patient lived in a nursing home prior to admission to the hospital, in which case the patient will be characterized based on resumption of normal activities.

INSIGHT 006: FLU-IVIG

A proportional odds model will be used to estimate a summary odds ratio. The model will include an indicator for treatment and indicators for the patient's clinical state at entry (ICU, general ward on supplemental oxygen, general ward not on supplemental oxygen). The model will be stratified by geographic region (United States, Europe, South America and Australasia).

To supplement the overall summary odds ratio, separate odds ratios will be estimated for each dichotomized definition of improvement that can be formulated from the components of the ordinal outcome. A test for the proportionality assumption will also be made.

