The following clinical secondary outcomes are of interest: 1) percent alive and out of the hospital at Day 14; 2) change in NEW score at Day 3; and 3) resumption of normal activities at Day 14. It is expected that IVIG will have a favorable effect on each of these outcomes as well as the ordinal primary outcome. Since the primary endpoint and these secondary endpoints are related and expected to be correlated, before examining each secondary endpoint separately, a single global test will be carried out using the method described by O'Brien and Pocock. ^{45,46} With this approach, the endpoints will be equally weighted and a single global test statistic will be determined. This single global test is expected to have greater power than the test for each endpoint separately. For example, for a common correlation among the four outcomes of 0.50, the average Z value must be 1.55 (instead of 1.96) to achieve a significance level of 0.05. The combined evidence using all four outcomes does not have to be as extreme as for a single outcome.

Time to death and time to hospital discharge will be summarized with Kaplan-Meier plots and Cox models. For time-to-event analyses, time will be measured from randomization. The comparison of NEW scores and HAI titers will be compared using analysis of covariance with the baseline score or titer as a covariate. HAI titer levels will be log-transformed and the data at each time point will be summarized as the ratio of geometric means for those assigned IVIG and placebo.

Longitudinal random effects models will also be used to summarize repeated assessments of the ordinal outcome, HAI titers and the NEW score. By collecting specific dates when patients are removed from the ICU and oxygen, discharged and resume normal activities, the ordinal outcome can be defined for a patient on each day of follow-up.

Symptoms reported and AEs will be compared for the IVIG and placebo groups and summarized using chi-square statistics. Laboratory measurements will be summarized as changes from baseline to Day 7.

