- The subgroup of participants with influenza A infection is identified as a key subgroup for whom the benefit is expected to exceed that of the overall group randomized (i.e., the treatment effect for those with influenza A is expected to be greater than for with influenza B infection) (see section C.). Power is estimated for the subgroup with influenza A.
- Outcomes other than the primary endpoint are divided into key secondary endpoints, supportive efficacy endpoints, and safety endpoints. The three key secondary endpoints are listed in terms of their importance.

B. Protocol summary and history

FLU-IVIG is a randomized, double blind multicenter, international clinical trial. Hospitalized patients with a National Early Warning (NEW) score of 2 or greater will be randomized in a 1:1 allocation ratio to either IVIG plus standard of care (SOC) therapy or to placebo for IVIG (a comparable volume of normal saline) plus SOC, and followed for 28 days. A total of 320 adult patients were to be enrolled over multiple influenza seasons. A schematic of the design is given below.

FLU-IVIG Design
Hospitalized Adults with Influenza A or B

The primary endpoint is an ordinal outcome at Day 7 that has 6 mutually exclusive categories:

1. Death
2. In the intensive care unit (ICU);
3. Non-ICU hospitalization, requiring supplemental oxygen;
4. Non-ICU hospitalization, not requiring supplemental oxygen;
5. Discharged, but unable to resume normal activities; or
6. Discharged with full resumption of normal activities.

Sample size was estimated assuming the following:

- A proportional odds model would be used to compare the IVIG and placebo groups for the primary ordinal outcome.⁴
- Type 1 error of 0.05 (2-sided) and power=0.80 to detect an odds ratio of 1.77 (an odds ratio greater than 1.0 corresponds to a more favorable response to IVIG than placebo).

For the primary analysis, in addition to a treatment indicator, the model will include indicators for whether the participant was enrolled in the ICU or general ward and whether oxygen was required, and will be stratified by geographic region.

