- If central laboratory results are negative or indeterminate for influenza strain/subtype, the local laboratory result will be used for classifying strain/subtype.
- Influenza vaccination was recorded differently on different versions of the baseline case report form. Participants will be considered as vaccinated if they report being vaccinated in the past 6 months or report being vaccinated in the season of their enrollment.
- IVIG lot will be imputed for participants assigned to placebo using the lot of the closest (in time) enrolled participant who received IVIG at that site.
- For the risk score for hospitalization or death at day 7, the following baseline covariates will be considered: age, gender, race/ethnicity, geographic region, duration of symptoms prior to enrollment, status at enrollment (ICU, general ward on O₂, general ward not on O₂), vaccination in current season, influenza strain, comorbidities (see above), other conditions (see above), and season of enrollment. The score for each participant will be determined using a logistic model that includes participants from both treatment groups.

The interaction between each subgroup and treatment will be assessed with expanded proportional odds models. Terms for each subgroup and a cross-product term with treatment will be added to the proportional odds model described above for the primary analysis. Interaction p-values for age, duration of symptoms, risk score for hospitalization or death at day 7, and NEW score will be based on the measured variable (1 df) not the categorical variable.

G. Secondary Endpoints

Some new secondary efficacy endpoints were defined, some in the protocol were dropped, and some are now defined as supportive. Reasons for this are:

- Approximately 40% of participants were discharged by day 3.
- The NEW score at day 3 was only determined for hospitalized participants. Thus, measuring change in NEW score at day 3 (as originally defined in the

protocol) is potentially biased due to missing data.

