Outcome at Day 3	FLU IVIG Pooled Outcome Data at Day 3 (N=324)	Outcome at Day 3	FLU IVIG Pooled Outcome Data at Day 3 (N=323)
Death	0.3	Death	0.3
ICU	6.5	ICU	6.5
Non-ICU hospitalization, NEW score ≥ 3	17.3	Non-ICU hospitalization, on O ₂	21.4
Non-ICU hospitalization, New score < 3	34.0	Non-ICU hospitalization, not on O ₂	30.0
Discharged	42.0	Discharged, not back to normal activities	34.7
Not applicable (NA)	NA	Discharged, back to normal activities	7.1

In summary, with both the 5-category and 6-category day 3 ordinal outcomes, the odds ratio which can be detected with power=0.80 is approximately 1.77 (assuming 324 participants and a 2-sided type 1 error of 0.05). This is very similar to the odds ratio specified in the design (1.77) for day 7. Even if the proportional odds assumption is violated, power is expected to be similar to 0.80 if the overall assumed odds ratio is maintained. However, considering the category percentages in Tables 2 for day 7 and in Table 5 for day 3, the significance of the final result is likely to be more heavily influenced by differences in the non-ICU hospitalization and discharge (overall or not back to normal) categories at day 3 and by the differences in the two discharge categories (not back to normal and back to normal) at day 7.⁹

Analysis Considerations for the Key Secondary Outcomes

The analysis of the day 3 ordinal outcomes will follow the same plan as for the primary ordinal outcome at day 7. Logistic regression will be used to summarize the difference between the IVIG and placebo group in the favorable outcome at day 7. This model will be stratified by geographic region and include indicators for the participant's clinical status at entry (ICU, general ward on supplemental oxygen, general ward not on supplemental oxygen), and an indicator for whether the participant was in the IVIG pilot trial (FLU 005) or the FLU-IVIG trial (FLU 006).

For participants in the IVIG Pilot, the NEW score was not collected. It will be estimated using the reported vital signs each day. Level of consciousness was not collected. It will be assumed to be zero, therefore NEW scores for these participants may be underestimated. For participants in FLU-IVIG (FLU 006), NEW scores were to be collected twice daily through day 3 while hospitalized. Thus, the NEW score on day 3

will use the average of 2 readings if available, otherwise the single reading collected will be used.

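### The primary model adjusts for entry state and region but not for age or symptom duration, and the day 3 NEW-based outcome is not adjusted for baseline NEW score; a cheap gain in efficiency is left unused

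*SAP*

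**What the plan says.** **Primary model.** SAP I.B: "in addition to a treatment indicator, the model will include indicators for whether the participant was enrolled in the ICU or general ward", with a further indicator for oxygen and stratification by region. Protocol 3.6 and 6.1 agree; 6.1 adds that "The model will be stratified by geographic region (United States, Europe, South America and Australasia"). The SAP's introduction lists its departures from the protocol, and no added covariate is among them. Part of SAP section E, where the model would be set out in full, was not in the text available for this review. The SAP's logistic models carry a pilot-trial indicator, and the primary model may carry one too.

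**Where age, duration and NEW score appear.** They are subgroup factors and baseline tabulations. SAP F tests their interactions with treatment as measured variables. The SAP also builds a day 7 risk score (hospitalization or death), for which "the following baseline covariates will be considered: age, gender, race/ethnicity, geographic region, duration of symptoms prior to enrollment", among others. NEW score is not on that list; entry state and region are on it and are also in the primary model.

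**Day 3 outcome.** In SAP G the first-listed key secondary outcome has five categories, two of which divide non-ICU inpatients at a day 3 NEW score of 3. "The analysis of the day 3 ordinal outcomes will follow the same plan as for the primary ordinal outcome at day 7". Protocol 6.1, by contrast, had NEW scores "compared using analysis of covariance with the baseline score or titer as a covariate".

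**The concern.** In a proportional odds model, leaving out a prognostic covariate pulls the treatment odds ratio toward 1 and costs power. Including one also removes chance imbalance in that variable. Age and symptom duration are plausible predictors of day 7 status, are already on the case report form, and cost almost nothing in degrees of freedom.

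The day 3 outcome is the clearer case. Its two NEW-defined categories hold 17.3% and 34.0% of pooled participants (SAP Table 5), 51.3% together. A patient's baseline NEW score would be expected to carry information about which of the two the patient falls in. The SAP adjusts viral load and HAI titer for their baseline values, but once the NEW comparison was recast as an ordinal outcome the baseline score dropped out of its model.

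There is little power to spare. The analysed set is 308 rather than 320, and SAP I.C gives power of only 0.67 at an odds ratio of 1.77 for the influenza A objective.

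**Working it through.** **1. Reproduce the plan's figure.** Inputs from Protocol 3.6 and Table 2: "The planned sample size for the trial is 320 randomized patients"; "Type 1 error is 0.05 (2-sided) and power =0.80"; "Patients will be equally allocated to IVIG or placebo"; odds ratio 1.77; placebo percentages 1.8, 3.6, 15.6, 14.1, 39.0, 25.8. The Whitehead formula for 1:1 allocation is

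N = 12 (z₀.₉₇₅ + z₀.₈₀)² / [ (ln OR)² (1 − Σ p̄³) ],

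where p̄ is the mean of the two arms' proportions in each category.

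- Shifting the placebo column by 1.77 gives an IVIG column of 1.0, 2.1, 9.9, 10.4, 38.4, 38.1, within 0.1 point of Table 2.
- The mean proportions are 0.014, 0.029, 0.128, 0.122, 0.387, 0.320, so Σ p̄³ = 0.0948.
- (ln 1.77)² = 0.3260 and (1.960 + 0.842)² = 7.849.
- N = 12 × 7.849 / (0.3260 × 0.9052) = 319.1. Power at 320 is 0.801.

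The formula contains no covariates, so their omission does not disturb the stated figure.

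**2. Same formula at other sizes.** Power = Φ( √[N (1 − Σ p̄³)/12] × ln OR − 1.960 ).

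- N=308: Φ(2.752 − 1.960) = 0.786.
- N=232 (influenza A): Φ(2.389 − 1.960) = 0.666, against the SAP's 0.67.

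**3. Gain from adding covariates.** The documents do not give the prognostic strength of the omitted variables beyond entry state and region, so it is an assumption. It is expressed as the SD of their combined log-odds predictor, from 0 to 1.0. Proportional odds models were simulated with 1,500 trials per setting (Monte Carlo error about 1 point). The covariates already in the model were given an assumed log-odds SD of 0.8, three further covariates were added, and the treatment effect was set so that the planned model shows an odds ratio of about 1.77. At N=308:

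| SD of omitted predictors | Latent R² | Power, planned model | Power, with added covariates | Gain (points) |
|---|---|---|---|---|
| 0 | 0 | 0.763 | 0.759 | none |
| 0.3 | 0.022 | 0.767 | 0.776 | 1 |
| 0.5 | 0.060 | 0.779 | 0.803 | 2 |
| 0.8 | 0.140 | 0.777 | 0.837 | 6 |
| 1.0 | 0.203 | 0.750 | 0.867 | 12 |

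With the effect fixed instead at 1.77 in the fuller model, the gains are 2 (0.717 to 0.735), 5 (0.721 to 0.771), 8 (0.691 to 0.768) and 11 points (0.641 to 0.751) at SDs 0.3, 0.5, 0.8 and 1.0.

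A separate simulation with 6,000 runs per setting and SDs of 0.4, 0.6 and 0.8 gave 0.77 to 0.79, 0.76 to 0.81 and 0.75 to 0.83 at N=308. At N=232 it gave 0.66 to 0.67, 0.65 to 0.69 and 0.64 to 0.72. Type I error was 0.048 to 0.052 in both models.

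**4. Rough cross-check.** Replacing N by N/(1 − R²) in step 2 at N=308 gives 0.806, 0.827, 0.847 and 0.868 for R² of 0.05, 0.10, 0.15 and 0.20, against 0.786 at R² = 0. This is the same order of gain, though smaller than the simulation at the strong end.

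**5. Change of scale.** At SD 0.8 and N=308 the estimated odds ratio moves from about 1.78 in the planned model to 1.91 in the fuller one.

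The simulations concern the day 7 outcome. No power figure was derived for adding baseline NEW score to the day 3 model.

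**The case against.** **This is a preference, not an error.** Correct. The plan follows the protocol, already adjusts for entry severity and region, and its power figure stands. A reader might infer that the trial is underpowered because of the omission; step 1 shows that the sample size never relied on covariates.

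**The gain is assumed.** Also correct. The risk-score variables are only to be considered, so the SAP does not establish age or duration as predictors. The true gain could be nil. What survives is the asymmetry: at SD 0 the change is within 0.5 point.

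**NEW score is a poor candidate.** A reader might infer that NEW score belongs in the primary model on the same footing, at no cost. The documents do not support that. SAP G says it was not collected in the 16 pilot participants. SAP D reports altered screening vital signs in 13 participants beyond the 17 excluded. Supplemental oxygen, already in the model, is itself a NEW component (Protocol Table 3). Leaving NEW score out keeps doubtful values away from the primary test.

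**The day 3 endpoint is a new one.** SAP G explains why change in NEW score was replaced: about 40% were discharged by day 3 and had no score. Not carrying the covariate over is therefore no contradiction. It is still a missed opportunity, because about half the participants are classified by that score.

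**The model text may be incomplete.** The available text cannot fully exclude a covariate named only in SAP E. Three concordant statements of the model, and a list of departures that mentions none, make it unlikely.

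**Conclusion.** The point holds as an efficiency improvement. In all the available text the primary model leaves out age and symptom duration, and the NEW-based day 3 outcome is analysed without baseline NEW score. Nothing stated in the plan is thereby wrong.

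For the primary outcome at N=308 the gain from adjustment is between none and about 12 points of power. It is about 1 to 2 points if the omitted variables are weakly prognostic (SD 0.3), 2 to 5 at SD 0.5 and 6 to 8 at SD 0.8. The range rests on an assumed prognostic strength, on normally distributed covariates independent of those already in the model, and on a true proportional odds effect near 1.77. It was simulated with three added covariates; with age and duration alone, the relevant row is the one matching whatever strength those two carry.

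**What to change.** Before unblinding:

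- **Primary model.** Prespecify age and days since symptom onset, both continuous, alongside entry state and region, and apply the same model to the influenza A analysis. Report the model with entry state and region only as a supporting analysis.
- **5-category day 3 model.** Add baseline NEW score. For the 16 pilot participants, estimate it from vital signs, as SAP G already does for their day 3 score. At the Thailand site, use the readings before alteration where they can be recovered, and state in advance what is done where they cannot. That rule must also cover the 17 participants whom the third sensitivity analysis brings back.
- **NEW score in the primary model.** Sensitivity analysis only.

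**Cost.** No new data collection: a sentence for age and duration, and a short paragraph for the NEW score rules. Enrolment has ended and pooled outcomes have been seen, but the SAP's authors are described as blinded, so the choice can still be made without knowledge of results by arm. The odds ratio becomes conditional on more covariates and is no longer directly comparable with 1.77; the supporting analysis preserves that comparison.

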Version 1.0 of the protocol was available on September 5, 2014. Version 2.0 of the protocol was released on May 31, 2016. The major change with version 2.0 was to remove the following exclusion criterion due to confusion among the clinical sites: “Strong clinical evidence (in the judgment of the site investigator) that the etiology of illness is primarily bacterial in origin.” In addition, the 5th inclusion criterion was changed to: “Hospitalized (or in observation unit) with influenza, with anticipated

hospitalization for more than 24 hours.” The sentence stating “Criteria for hospitalization will be up to the individual treating clinician” was removed.

As mentioned in the protocol (section 6.2), a sample size re-estimation using pooled outcome data at day 7 was to be carried out when approximately 50% of patients had been enrolled. The sample size re-estimation was carried out in August 2017 when 53% of the 320 planned participants (170) had day 7 primary outcome data.

The FLU-IVIG trial was overseen by an independent Data and Safety Monitoring Board (DSMB) appointed by NIAID. The DSMB last met on January 18, 2018.

C. Trial Objectives

The primary objective is to compare the clinical status of participants in the IVIG and placebo groups at day 7 of follow-up using the previously defined 6-category primary ordinal outcome. Other efficacy outcomes and safety outcomes will also be evaluated.

Over the course of the trial, 5 batches of IVIG were prepared. Laboratory testing of the IVIG indicated that HAI titers were substantially greater for influenza A strains than influenza B strains. Whether the HAI titers of the IVIG are good surrogates for the clinical response is uncertain. However, it is biologically plausible that the benefit of IVIG on the day 7 clinical outcomes will be greater for participants infected with influenza A as compared to influenza B as a consequence of the IVIG used.

Thus, the main secondary objective is to compare the clinical status of participants infected with influenza A virus in the IVIG and placebo groups at day 7 of follow-up using the 6-category primary ordinal outcome.

The null hypothesis for the primary and main secondary objective is that there is no difference between the IVIG and placebo group in the day 7 primary ordinal outcome.

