Sample size for the primary objective (N=320; 160 per group) assumed equal allocation of participants to each treatment, type 1 error of 0.05 (2-sided), power=0.80 to detect an odds ratio of 1.77

Category percentages assumed in the design and given in the protocol are shown below in Table 1 for the primary ordinal outcome.

In the discussion that follows, unless otherwise stated, the numbers shown for both treatment groups combined include the 16 participants from the IVIG pilot study. These results are referred to as “FLU IVIG Pooled Outcome Data”.

Table 1

Outcome at Day 7	Percent in Each Category	
	IVIG	Placebo
Death	1.0	1.8
ICU (for FLU 003, assumed those ventilated were in the ICU)	2.1	3.6
Non-ICU hospitalization, O ₂	9.9	15.6
Non-ICU hospitalization, no O ₂	10.3	14.1
Discharged, not back to normal activities	38.4	39.0
Discharged, back to normal activities	38.2	25.8

As previously mentioned, the pooled FLU IVIG outcome data at day 7 after 170 participants were enrolled are similar to pooled data used in the design (see Table 2 below).

Table 2

Outcome at Day 7	Percent in Each Category	
	FLU IVIG Pooled Outcome Data (N=170)	Average of Design Estimates for the IVIG and Placebo Groups
Death	1.8	1.4
ICU	7.1	2.9
Non-ICU hospitalization, O ₂	10.6	12.8
Non-ICU hospitalization, no O ₂	7.6	12.2
Discharged, not back to normal activities	35.9	38.7
Discharged, back to normal activities	37.0	32.0

Pooled FLU IVIG outcome data (category percentages) at day 7 for 220 participants with influenza A infection as of April 30, 2018 are also similar to the overall category percentages above (see Table 3).

Table 3

Outcome at Day 7	FLU IVIG Pooled Outcome Data for Participants with Influenza A Infection (N=220)
Death	1.4
ICU	4.6
Non-ICU hospitalization, O ₂	10.5
Non-ICU hospitalization, no O ₂	8.2
Discharged, not back to normal activities	35.5
Discharged, back to normal activities	40.0

We assume that 232 of the participants ultimately randomized to FLU IVIG will be infected with influenza A. Assuming the design assumptions stated in the protocol and given in Table 1, with 232 participants, power is 0.67 to detect an odds ratio of 1.77 at the 0.05 level of significance (2-sided). An odds ratio of 1.95 can be detected with power=0.80 with 232 participants. The IVIG and placebo category percentages for participants with influenza A infection corresponding to an odds ratio of 1.95 are given in Table 4.

Table 4

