Outcome at Day 7	Participants with Influenza A; Assumed Percentages in Each Category	
	IVIG (N=116)	Placebo (N=116)
Death	1.0	1.8
ICU (for FLU 003, assumed those ventilated were in the ICU)	1.9	3.6
Non-ICU hospitalization, O ₂	9.1	15.6
Non-ICU hospitalization, no O ₂	9.7	14.1
Discharged, not back to normal activities	37.8	39.0
Discharged, back to normal activities	40.5	25.8

D. Analysis Set

The analysis set for the primary efficacy and safety analyses and all other analyses will exclude 21 randomized participants:

- 4 participants who declined to receive an IVIG/placebo infusion; and
- 17 participants at a single site in Thailand for whom eligibility based on the NEW score could not be confirmed and data alteration of the vital signs used to compute the NEW score was suspected.

One other participant (at a different site) did not meet strict eligibility criteria. This participant had a locally determined positive influenza test 4 days prior to randomization instead of within 2 days as stated in the protocol. This participant will be retained in the

primary analysis because this was not considered to be major, there was no evidence that it was intentional, and it is in keeping with the intention to treat principle. Thus, analyses in the final report will be restricted to 308 randomized participants. These analyses will be referred to as modified intention to treat.

For the primary efficacy analysis, missing day 7 outcomes (4 participants have missing outcomes among those infused) will be imputed for participants who were infused.

Sensitivity analyses will be carried out to assess the impact of including participants from the pilot study, to assess the impact of imputation for the primary outcome, and to assess the impact of the exclusion of participants from the site in Thailand.

The four sensitivity analyses are:

- 1) An analysis that excludes participants enrolled in the IVIG pilot (16 participants).
- 2) An analysis that excludes participants for whom the day 7 outcome is missing (4 participants).
- 3) An analysis that includes the 17 participants who may not have met the NEW score eligibility criteria at the site in Thailand.
- 4) An analysis that excludes all participants at the site in Thailand (80 total) for which the eligibility of 17 participants could not be confirmed.

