To supplement the overall summary odds ratio, separate odds ratios will be estimated for each dichotomized definition of improvement that can be formulated from the components of the ordinal outcome. A test for the proportionality assumption will also be made.

Analyses identical to those described above (including the imputation) will be carried out for participants with influenza A virus infection. If the central determination of influenza resulted in negative or indeterminate results, the local determination will be used. For participants with a co-infection with A and B influenza subtypes, the participant will be classified as A.

The analyses described above will be carried out for the primary efficacy analysis and for the two planned sensitivity analyses.

These analyses will be supplemented with summaries which give the category percentages for the primary ordinal outcome by treatment group for days 1-7.

F. Subgroup Analysis

Analyses will be carried out for the following baseline-defined subgroups:

- Influenza strain (A, B) and subtype (pH1N1, H3N2, B)
- Age (<40, 40-59, ≥ 60 years)
- Gender (men, women)
- Race/ethnicity (White/Hispanic/other, Black, Asian)
- Enrollment ward/use of O₂ (ICU, general ward on O₂, general ward not on O₂)
- Geographic region (United States/South America/Mexico, Europe/Australia, Thailand)
- Northern/Southern hemisphere/Equatorial (United States, Mexico, and Europe vs Australia and South America vs Thailand)
- Duration of symptoms prior to randomization (≤ 3, 4, ≥ 5 days)
- New score (≤ 3, 4-5, ≥ 6)
- Influenza season (Oct2013-Sep2014, Oct2014-Sep2015, Oct2015-Sep2016, Oct2016-Sep2017, Oct2017-Jun2018)
- Co-morbidities (CVD, COPD/asthma, diabetes, none of these) (as hierarchy)
- Other conditions (sepsis, pneumonia, immune suppression) (each considered separately versus not having the condition)

- Influenza strain/viral load (A and viral load > 100,000/≤ 100,000, B and viral load > 1,000,000/≤ 1,000,000) (4 categories)
- Influenza vaccination (yes, no, unknown)
- Smoking status (current smoker, non-smoker)
- IVIG lot (1-5)
- HAI titer (highest titer measured)
- HAI titer corresponding to subtype of infection (highest titer measured)
- Risk score tertile for hospitalization or death at day 7

The following special situations will apply to the categorization of participants for subgroup analyses:

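### Does the SAP need to say what a significant influenza A result means if the overall Day 7 test is not significant?

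*SAP*

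**What the plan says.** SAP section C states one primary objective: comparing the IVIG and placebo groups on the six-category ordinal outcome at Day 7, in all participants. It then notes that HAI titers in the IVIG product were much higher against influenza A than against B, and continues: "Thus, the main secondary objective is to compare the clinical status of participants infected with influenza A virus in the IVIG and placebo groups". One sentence gives the null for both: "The null hypothesis for the primary and main secondary objective is that there is no difference between the IVIG and placebo group".

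Section I.A lists this as a declared departure from the protocol. Influenza A is "identified as a key subgroup for whom the benefit is expected to exceed that of the overall group randomized". In Protocol 6.1, influenza subtype was only one of eight subgroup factors, each with a heterogeneity test.

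On size, section C says: "We assume that 232 of the participants ultimately randomized to FLU IVIG will be infected with influenza A". It gives power of 0.67 at an odds ratio (OR) of 1.77 and 0.80 at 1.95, both at two-sided 0.05. Section D removes 21 participants: "Thus, analyses in the final report will be restricted to 308 randomized participants". Section E repeats the primary analysis in influenza A. Section F lists strain among the subgroups and adds: "The interaction between each subgroup and treatment will be assessed with expanded proportional odds models".

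The text available for review contains no testing order or alpha split, and no statement that the influenza A result is descriptive. Part of section E was not in that text and may bear on the point.

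**The concern.** Influenza A has been raised from one subgroup factor among eight to the main secondary objective. It shares a null-hypothesis sentence with the primary objective, and its power is quoted at the full 0.05 level. Suppose the overall test misses and influenza A reaches p<0.05. One author could report a prespecified main secondary objective as met; another could report a nominal subgroup finding. If nothing in the plan decides between them, the choice is made with the data in view.

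The case is not remote. The SAP expects a larger effect in A, and a diluted overall result with a significant A result is the pattern that expectation would produce. A second worry is that a significant strain interaction might then be taken as confirmation, although the interaction test has little power at this size.

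**Working it through.** **Inputs.** Placebo percentages from SAP Table 1 (1.8, 3.6, 15.6, 14.1, 39.0, 25.8), used for both strains; N = 320 planned and 308 analysed; influenza A n = 232 among those randomized. The influenza A count among the 308 is not given. Removing none to all of the 21 exclusions gives 232 to 232 − 21 = 211; an even spread gives 232 × 308/329 = 217. Covariates are ignored. Odds ratios for influenza B are assumptions.

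**Reproducing the SAP's power.** Ordinal-data (Whitehead) information is V = n/12 × (1 − Σ p̄³), where p̄ is the mean of the two arms' category shares. Power = Φ(ln OR × √V − 1.96).

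| n | OR | 1 − Σp̄³ | V | ln OR × √V | Power | SAP |
|---|---|---|---|---|---|---|
| 320 | 1.77 | 0.905 | 24.14 | 2.805 | 0.801 | 0.80 |
| 232 | 1.77 | 0.905 | 17.50 | 2.389 | 0.666 | 0.67 |
| 232 | 1.95 | 0.903 | 17.46 | 2.791 | 0.797 | 0.80 |

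The SAP's figures hold. At N = 308 and OR 1.77, overall power is 0.786.

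**Error rate if influenza A were a second confirmatory test.** The overall and influenza A statistics are correlated, with r = √(n_A/308) = 0.828, 0.839 and 0.868 for n_A = 211, 217 and 232. Under the null, P(A significant, overall not) = 0.0262, 0.0254 and 0.0232. Adding the primary test's 0.05 gives a chance of any false positive of 0.076, 0.075 and 0.073. If A is nominal, or is tested only after a significant overall result, the confirmatory error stays at 0.05.

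**How often the pattern arises, and what the interaction test adds** (normal simulation, 4,000,000 draws per case; ranges run over n_A = 211–232; the joint rate is A alone significant together with interaction p<0.05).

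| OR in A, in B | A alone significant | Interaction p<0.05, given A alone | Joint rate |
|---|---|---|---|
| 1.0, 1.0 | 2.3–2.6% | 34–38% | 0.8–1.0% |
| 1.77, 1.77 | about 2.4% | 18–19% | 0.4–0.5% |
| 1.95, 1.3 | 7–9% | 36–39% | 2.5–3.4% |
| 1.95, 1.0 | 14–19% | 53–58% | 8–11% |

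The conditional 34–38% under the null looks alarming, but it applies to an event seen in 2.3–2.6% of null trials. The joint pattern is roughly ten times as frequent when benefit is confined to A as under the null. The interaction test's own power is 29–32% at 1.95 and 1.0, and 14–15% at 1.95 and 1.3, so a non-significant interaction would say little.

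**Cost of a formal rule.** Testing A only after a significant overall result leaves overall power at 0.79 but forfeits a formal claim in 14–19% of trials if benefit is confined to A. An equal split that holds 5% overall needs about 0.032–0.034 per test. At 0.033, overall power falls from 0.79 to 0.73 and influenza A power at OR 1.77 from 0.62–0.67 to 0.56–0.60.

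**The case for a change.** The best case for a change is that the word secondary gives rank but no decision rule. The statement that the key secondary endpoints are listed by importance covers endpoints, not the influenza A objective, and section F gives the interaction test no part in reading an influenza-A-only result. One sentence written before unblinding would cost nothing and would remove a choice that could otherwise be made after seeing the data. This stands as good practice.

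It does not show that the plan, followed as written, misleads. Population, outcome, model, expected direction and rank were fixed by blinded statisticians and the protocol co-chairs. Influenza A received a power statement, not a share of alpha, and nothing in the text reviewed lets it rescue a failed primary. The two competing descriptions also overlap: a result can be both a prespecified secondary objective and nominal. Nor does any visible text treat the interaction test as confirmation.

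A related point is that Protocol 6.1 calls for a global test before the secondary endpoints are examined singly, and the SAP text reviewed does not say whether it survives. One of its components, change in NEW score at Day 3, was set aside as potentially biased, and the two Day 14 components became supportive. Sections I.A and G disclose this regrouping, so the test cannot run as described. It concerns endpoints in all participants rather than strain, and is a record-keeping matter.

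**Conclusion.** No change is needed. The SAP ranks the two comparisons clearly enough that an analyst would report an influenza-A-only result as nominal, with its confidence interval, the influenza B estimate and the planned interaction test. The primary test's 5% error is untouched. The extra 2.3–2.6 percentage points of false-positive risk arise only if someone gives influenza A a confirmatory standing that the SAP does not give it. Adopting a formal rule is a trade-off: gating loses claims where the SAP most expects benefit, and splitting alpha costs about five to seven points of power on each test.

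This rests on 211–232 influenza A participants among the 308, on Table 1 placebo percentages in both strains, and on assumed influenza B odds ratios of 1.0 to 1.77. Part of section E was not in the text reviewed; if it addresses the matter, even the optional clarification falls away.
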